6.3 Lifestyle Restrictions

Not applicable. No restrictions are required

6.4 Screen Failures

Screen failures are defined as participants who consent to participate in the clinical study but are not subsequently entered in the study. A minimal set of screen failure information is required to ensure transparent reporting of screen failure participants, to meet the Consolidated Standards of Reporting Trials (CONSORT) publishing requirements, and to respond to queries from regulatory authorities. Minimal information includes date of consent, demography, screen failure details, eligibility criteria, and any serious AEs.

6.4.1 Retesting During Screening or Lead-In Period

Participant Re-enrollment: This study permits the re-enrollment of a participant that has discontinued the study as a pre-treatment failure (ie, participant has not been randomized / has not been treated). If re-enrolled, the participant must be re-consented.

Retesting of laboratory parameters and/or other assessments within any single Screening or Lead-in period will be permitted (in addition to any parameters that require a confirmatory value).

The most current result prior to Treatment assignment is the value by which study inclusion will be assessed, as it represents the participant's most current clinical state.

Laboratory parameters and/or assessments that are included in [Table 2-1](#), Screening Procedural Outline may be repeated in an effort to find all possible well-qualified participants. Consultation with the Medical Monitor may be needed to identify whether repeat testing of any particular parameter is clinically relevant.

7 TREATMENT

Study treatment is defined as any investigational treatment(s), marketed product(s), placebo or medical device intended to be administered to a study participant according to the study treatment assignment or treatment allocation. Study treatment includes both Investigational [Medicinal] Product (IP/IMP) and Non-investigational [Medicinal] Product (Non-IP/Non-IMP) and consist of the following:

- Nivolumab
- Ipilimumab

An investigational product, also known as investigational medicinal product in some regions, is defined a pharmaceutical form of an active substance or placebo being tested or used as a reference in a clinical study, including products already with a marketing authorization but used or assembled (formulated or packaged) differently than the authorized form, or used for an unauthorized indication, or when used to gain further information about the authorized form.

Other medications used as support or escape medication for preventative, diagnostic, or therapeutic reasons, as components of the standard of care for a given diagnosis, may be considered as non-investigational products.

| Product Description / Class and Dosage Form | Potency | IP/ Non-IMP | Blinded or Open Label | Packaging / Appearance | Storage Conditions (per label) |
|--|----------------|--------------------|------------------------------|--|--|
| Nivolumab/BMS - 936558-01 Solution for Injection | 10 mg/ml | IP | Open Label | 240 mg kit or 5 or 10 (100mg) vials per carton; Clear to opalescent, colorless to pale yellow liquid; Few particulates may be present. | Store at 2-8°C; Protect from light and freezing. |
| Ipilimumab Solution for Injection | 5 mg/ml | IP | Open Label | 4 vials per carton; Clear, colorless liquid. Few particles may be present. | Store at 2-8°C; Protect from light and freezing. |

7.1 Treatments Administered

The selection and timing of dose for each participant is as follows:

Table 7.1-1: Selection and Timing of Dose

| Study Treatment | Unit dose strength(s)/Dosage level(s) | Dosage formulation Frequency of Administration | Route of Administration |
|------------------------|--|---|--------------------------------|
| Nivolumab | 240 mg | Every 2 weeks | IV |
| Ipilimumab | 1 mg/kg | Every 6 weeks | IV |

Participants will receive treatment with nivolumab 240 mg as a 30 minute infusion every 2 weeks and ipilimumab 1 mg/kg as a 30 minute infusion every 6 weeks, starting on Day 1, until progression, unacceptable toxicity, withdrawal of consent, 24 months from first dose, or the study ends, whichever occurs first. Participants should begin study treatment within 3 calendar days of treatment assignment.

When nivolumab and ipilimumab are to be administered on the same day, nivolumab is to be administered first. Nivolumab infusion must be promptly followed by a flush of diluent to clear the line of nivolumab before starting the ipilimumab infusion. The second infusion will always be the ipilimumab study treatment and will start after the infusion line has been flushed, filters changed and patient has been observed to ensure no infusion reaction has occurred.

Nivolumab and ipilimumab may be diluted in 0.9% Sodium Chloride solution or 5% Dextrose solution.

Dosing calculations for ipilimumab should be based on the body weight. If the participant's weight on the day of dosing differs by > 10% from the weight used to calculate the prior dose, the dose must be recalculated. All doses should be rounded to the nearest milligram. There will be no dose modifications allowed.

There are no premedications recommended.

Participants should be carefully monitored for infusion reactions. If an acute infusion reaction is noted, participants should be managed according to [Section 7.4.3](#).

Doses of nivolumab and/or ipilimumab may be interrupted, delayed, or discontinued depending on how well the participant tolerates the treatment. For more details, see Sections 7.4.1 (dose delays), 7.4.3 (resuming treatment), and 8.1 (discontinuation).

7.2 Method of Treatment Assignment

All participants will be centrally assigned to treatment using an Interactive Response Technology (IRT). Before the study is initiated, each user will receive log in information and directions on how to access the IRT. Study treatment will be dispensed at the study visits as listed in Schedule of Activities ([Section 2](#)).

7.3 Blinding

Not applicable. This is an open-label study, and therefore blinding procedures are not applicable.

7.4 Dosage Modification

7.4.1 Dose Delay Criteria for Cohorts A, B, and C

Nivolumab and ipilimumab administration should be delayed for the following:

- Grade 2 non-skin, drug-related AE, except for fatigue
- Grade 3 skin, drug-related AE
- Grade 2 drug-related creatinine, AST, ALT and/or total bilirubin abnormalities
- Grade ≥ 3 drug-related laboratory abnormality, with the following exceptions:
 - Grade 3 lymphopenia or asymptomatic amylase or lipase does not require a dose delay
 - Grade ≥ 3 AST, ALT, Total Bilirubin will require dose discontinuation
- Any AE, laboratory abnormality or inter-current illness which, in the judgment of the investigator, warrants delaying the dose of study medication.
- Participants receiving ipilimumab in combination with nivolumab that have drug-related toxicities that meet the criteria for dose delay, should have both drugs (ipilimumab and nivolumab) delayed until retreatment criteria are met. (Exceptions apply to the retreatment criteria after dose delay of ipilimumab and nivolumab for Grade 4 amylase and lipase abnormalities that are not associated with symptoms or clinical manifestations of pancreatitis and that are attributed to ipilimumab alone.)

Participants who require delay should be re-evaluated weekly or more frequently if clinically indicated and resume study medication dosing when re-treatment criteria are met.

Rescheduling:

- Nivolumab may be delayed until the next planned ipilimumab dose if the next ipilimumab dose is scheduled within the next 12 days. This will permit periodic ipilimumab dosing to be synchronized with nivolumab dosing.

- Ipilimumab should be dosed at the specified interval regardless of any delays in intervening nivolumab doses. However, in order to maintain periodic synchronized dosing of ipilimumab and nivolumab, the dosing days of nivolumab and ipilimumab may be adjusted within the permitted ± 5 day window, as long as consecutive nivolumab doses are given at least 12 days apart. Ipilimumab may be delayed beyond the 5 day window if needed to synchronize with the next nivolumab dose.
- If an ipilimumab dose is delayed beyond 6 weeks from the prior ipilimumab dose, then subsequent ipilimumab doses should be rescheduled to maintain the 6 week interval between consecutive ipilimumab doses.
- A dose delay of ipilimumab which results in no ipilimumab dosing for > 12 weeks requires ipilimumab discontinuation, with exceptions as noted in [Section 8.1.1.2](#).

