8.1.1 Study Drug Discontinuation

8.1.1.1 Nivolumab Discontinuation for Cohorts A, B, and C

Nivolumab treatment should be permanently discontinued for the following:

- Any Grade 2 drug-related uveitis, eye pain or blurred vision that does not respond to topical therapy and does not improve to Grade 1 severity within the re-treatment period OR requires systemic treatment
- Any Grade 3 non-skin, drug-related AE lasting > 7 days, or recurs with the following exceptions for laboratory abnormalities, diarrhea, colitis, neurologic toxicity, drug-related uveitis, pneumonitis, bronchospasm, hypersensitivity reactions, infusion reactions, and endocrinopathies:
 - Grade 3 drug-related diarrhea, colitis, neurologic toxicity, uveitis, pneumonitis, bronchospasm, myocarditis, hypersensitivity reaction, or infusion reaction of any duration requires discontinuation

- Grade 3 drug-related endocrinopathies, adequately controlled with only physiologic hormone replacement do not require discontinuation. Adrenal insufficiency requires discontinuation regardless of control with hormone replacement.
- Grade 3 drug-related laboratory abnormalities do not require treatment discontinuation except:
 - ◆ Grade 3 drug-related thrombocytopenia > 7 days or associated with bleeding requires discontinuation
 - ◆ Any drug-related liver function test (LFT) abnormality that meets the following criteria require discontinuation:
 - Grade ≥ 3 drug-related AST, ALT or Total Bilirubin requires discontinuation*
 - Concurrent AST or ALT > 3 x ULN and total bilirubin > 2x ULN

*In most cases of Grade 3 AST or ALT elevation, study treatment will be permanently discontinued. If the investigator determines a possible favorable benefit/risk ratio that warrants continuation of study treatment, a discussion between the investigator and the BMS Medical Monitor/designee must occur.

- Any Grade 4 drug-related adverse event or laboratory abnormality (including but not limited to creatinine, AST, ALT, or Total Bilirubin), except for the following events which do not require discontinuation:
 - Grade 4 neutropenia ≤ 7 days
 - Grade 4 lymphopenia or leukopenia or asymptomatic amylase or lipase
 - Isolated Grade 4 electrolyte imbalances/abnormalities that are not associated with clinical sequelae and are corrected with supplementation/appropriate management within 72 hours of their onset

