 - Grade 4 drug-related endocrinopathy adverse events, such as, hyper- or hypothyroidism, or glucose intolerance, which resolve or are adequately controlled with physiologic hormone replacement (corticosteroids, thyroid hormones) or glucose-controlling agents, respectively, may not require discontinuation after discussion with and approval from the BMS Medical Monitor.
- Any event that leads to delay in dosing lasting > 6 weeks for nivolumab from the previous dose requires discontinuation, with the following exceptions:
 - Dosing delays to allow for prolonged steroid tapers to manage drug-related adverse events are allowed.
 - Dosing delays lasting > 6 weeks for nivolumab from the previous dose that occur for non-drug-related reasons may be allowed if approved by the BMS Medical Monitor (or designee).

Prior to re-initiating treatment in a participant with a dosing delay lasting > 6 weeks, the BMS Medical Monitor (or designee) must be consulted. Tumor assessments should continue as per protocol even if dosing is delayed. Periodic study visits to assess safety and laboratory studies

should also continue every 6 weeks or more frequently if clinically indicated during such dosing delays.

Any adverse event, laboratory abnormality, or intercurrent illness which, in the judgment of the Investigator, presents a substantial clinical risk to the participant with continued nivolumab dosing.

The assessment for discontinuation of nivolumab should be made separately from the assessment made for discontinuation of ipilimumab. Although there is overlap among the discontinuation criteria, if discontinuation criteria are met for ipilimumab but not for nivolumab, treatment with nivolumab may continue if ipilimumab is discontinued.

If a participant meets criteria for discontinuation and investigator is unable to determine whether the event is related to both or one study drug, the participant should discontinue both nivolumab and ipilimumab and be taken off the treatment phase of the study. Continuation of ipilimumab after discontinuation of nivolumab is not allowed on study.

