8.1.1.2 Ipilimumab Dose Discontinuation for Cohorts A, B, and C

Ipilimumab must be permanently discontinued if any of the following criteria are met:

- Any Grade 2 drug-related uveitis or eye pain or blurred vision that does not respond to topical therapy and does not improve to Grade 1 severity within 2 weeks OR requires systemic treatment;
- Any Grade ≥ 3 bronchospasm or other hypersensitivity reaction;
- Any other Grade 3 non-skin, drug-related adverse event with the following exceptions for laboratory abnormalities, grade 3 nausea and vomiting, grade 3 neutropenia and thrombocytopenia, and symptomatic endocrinopathies (except for adrenal insufficiency) which resolved (with or without hormone substitution);
- Any drug-related LFT abnormality that meets the following criteria require discontinuation:
 - AST or ALT $> 8x$ ULN
 - Total bilirubin $> 5 x$ ULN
 - Concurrent AST or ALT $> 3 x$ ULN and total bilirubin $> 2 x$ ULN
- Any Grade 4 drug-related AE or laboratory abnormality, except for the following events, which do not require discontinuation:
 - Grade 4 neutropenia ≤ 7 days
 - Grade 4 lymphopenia or leukopenia
 - Isolated Grade 4 amylase or lipase abnormalities which are not associated with symptoms or clinical manifestations of pancreatitis. The BMS Medical Monitor should be consulted for Grade 4 amylase or lipase abnormalities.
 - Isolated Grade 4 electrolyte imbalances/abnormalities that are not associated with clinical sequelae and are corrected with supplementation/appropriate management within 72 hours of their onset
 - Grade 4 drug-related endocrinopathy AEs such as hyper- or hypothyroidism, or glucose intolerance, which resolve or are adequately controlled with physiologic hormone

replacement (corticosteroids, thyroid hormones) or glucose controlling agents, respectively, may not require discontinuation after discussion with and approval from the BMS Medical Monitor.

- Any treatment delay resulting in no ipilimumab dosing for > 12 weeks with the following exceptions: Dosing delays to manage drug-related AEs, such as prolonged steroid tapers, are allowed. Prior to re-initiating treatment in a participant with a dosing delay lasting > 12 weeks, the BMS medical monitor must be consulted. Tumor assessments should continue as per protocol even if dosing is delayed.

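### For isolated drug-related Grade 3 AST or ALT elevation, Section 7.4.1 requires discontinuation without exception, while the footnote in Section 8.1.1.1 lets study treatment continue after a discussion

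*Combined protocol and SAP*

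**What the plan says.** Four places in the protocol deal with drug-related liver test elevation in Cohorts A, B and C.

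- **Section 7.4.1 (dose delay).** The list opens with "Nivolumab and ipilimumab administration should be delayed for the following", so it governs both drugs. Under drug-related laboratory abnormalities of Grade 3 or higher, it says that for this grade "AST, ALT, Total Bilirubin will require dose discontinuation". No exception is attached.
- **Section 8.1.1.1 (nivolumab discontinuation).** The main line says that Grade 3 or higher "drug-related AST, ALT or Total Bilirubin requires discontinuation", and carries an asterisk. The footnote reads "In most cases of Grade 3 AST or ALT elevation, study treatment will be permanently discontinued", and adds that if the investigator sees a possible "favorable benefit/risk ratio that warrants continuation of study treatment, a discussion between the investigator and the BMS Medical Monitor/designee must occur". The same section ends with a rule linking the drugs: "Continuation of ipilimumab after discontinuation of nivolumab is not allowed on study".
- **Section 8.1.1.2 (ipilimumab discontinuation).** Laboratory abnormalities are exempted from the general Grade 3 rule. Ipilimumab must stop at "AST or ALT $> 8x$ ULN", at total bilirubin above 5 x ULN, or when AST or ALT above 3 x ULN occurs together with bilirubin above 2 x ULN.
- **Section 8.1.3 (additional guidance).** When a Section 7.4.1 liver condition is met, the investigator is to consider stopping. When a Section 8.1 condition is met, stopping is mandatory.

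Cohort A1 inherits these rules through Sections 7.4.1.1 and 8.1.1.3. The liver exceptions there are for participants with hepatic impairment.

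**The concern.** At the same Grade 3 AST or ALT value, one section mandates stopping and another allows treatment to go on. A third section describes the first as something to consider. No sentence says which prevails, so two sites can act differently and both point to the protocol.

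The trial exists to characterise toxicity, and hepatitis is one of the named select events in the primary endpoint. There is no data monitoring committee (Section 5.1.2), so consistent handling rests on the protocol text and the Medical Monitor. Further exposure after a Grade 3 liver event bears first on participant safety. It also bears on the discontinuation rate and on the time during which events are counted. Section 10.3.2 counts select events up to 30 days, and immune-mediated events up to 100 days, after the last dose, so continued dosing lengthens the counting period.

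**Working it through.** No sample size or error rate is involved. The check applies each passage to the same isolated, drug-related laboratory value.

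**Step 1: where Grade 3 starts.** Section 7.4.1.1 gives Grade 2 as above 3.0 to 5.0 x ULN for AST or ALT, and above 1.5 to 3.0 x ULN for bilirubin. Grade 3 therefore starts above 5.0 x ULN and above 3.0 x ULN respectively. The upper end of Grade 3 is not given in the documents.

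**Step 2: compare with the ipilimumab limits in Section 8.1.1.2.** For AST or ALT the limit is 8 x ULN against a Grade 3 start of 5 x ULN. For bilirubin it is 5 x ULN against 3 x ULN. The bands to test are AST or ALT above 5 and up to 8 x ULN, and bilirubin above 3 and up to 5 x ULN.

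**Step 3: ALT 6 x ULN, bilirubin normal.**

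| Text applied | Result |
|---|---|
| 7.4.1 | Both drugs stop |
| 8.1.1.1, main line | Nivolumab stops; the linking rule then stops ipilimumab |
| 8.1.1.1, footnote | Study treatment may continue after discussion |
| 8.1.1.2 alone | Ipilimumab is not required to stop |
| 8.1.3 | Stopping considered for the 7.4.1 condition, required for the 8.1 condition |

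On a full reading two outcomes remain: both drugs stopped, or study treatment continued.

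**Step 4: bilirubin 4 x ULN, AST and ALT normal.** Section 7.4.1 stops both drugs. Section 8.1.1.1 stops nivolumab, and the linking rule then stops ipilimumab. The footnote names only AST and ALT, so its wording gives no route to continue. Section 8.1.1.2 does not itself require ipilimumab to stop, but the linking rule settles that. Both drugs stop either way. The one loose end is that the asterisk sits on a line that also names bilirubin.

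**Step 5: AST 9 x ULN, assumed still Grade 3.** The footnote allows study treatment to continue, and Section 7 defines study treatment as both drugs. Section 8.1.1.2 requires ipilimumab to stop and carries no footnote. If the footnote is used, the two sections together leave nivolumab alone continuing, but the footnote does not say so.

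**Step 6: what role the ipilimumab limits have.** If nivolumab stops at Grade 3, ipilimumab stops with it. Within Grade 3, the limits of 8 x and 5 x ULN can therefore operate only when the footnote has been used, and Section 7.4.1 leaves no room for that.

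**The case against.** The best reply is that Section 8 governs discontinuation and is coherent on its own. Section 7.4.1 concerns delays. Section 7.1 sends the reader to 7.4.1 for delays and to 8.1 for discontinuation, and Section 7.4.5.2 closes by pointing to Section 8. Section 8.1 says the two drugs are assessed separately, so different limits per drug can be deliberate. The footnote is a marked exception to its own section. When it is used, the ipilimumab limits still apply to ipilimumab. The difference in force in Section 8.1.3 also points to Section 8 as controlling, and the Medical Monitor discussion is a central check.

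Much of this stands. Separate limits per drug are not a contradiction in themselves, and the footnote is not a free-standing rule. But the pointers do not cancel the mandatory line in Section 7.4.1, which a site can follow without ever meeting the footnote. Section 8.1.3 does not resolve the matter either, because it describes as optional what 7.4.1 states as required. The central check is also limited: the footnote asks for a discussion, whereas other exceptions, such as retreatment with persistent Grade 1 pneumonitis in Section 7.4.5.1, ask for the Medical Monitor's approval.

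It is also fair that the effect on the primary table may be small. Grades 3 and 4 are reported together, so a counted Grade 3 hepatic event that worsens to Grade 4 stays in the same category.

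**Conclusion.** The conflict is real but narrow. It concerns isolated, drug-related Grade 3 AST or ALT elevation in Cohorts A, B and C, and in A1 participants without hepatic impairment. Between 5 and 8 x ULN the outcomes are both drugs stopped or study treatment continued. Above 8 x ULN, if that is still Grade 3, the footnote and Section 8.1.1.2 also need to be reconciled for ipilimumab.

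A reader might infer three stronger points that the documents do not support.

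- **Only nivolumab stopped.** This follows only if Section 8.1.1.2 is read without the rule barring ipilimumab once nivolumab is discontinued.
- **The same divergence for bilirubin.** The footnote text does not name bilirubin, so both drugs stop on any full reading.
- **A count of affected participants.** Section 10.1 cites at most 5% high-grade events per category, which gives 0.05 x 400 = 20 in each of Cohorts A and B and 0.05 x 100 = 5 in Cohort C, or 45 of 900. That rate comes from an earlier study with 39 participants on this schedule. Section 3.2.4 reports skin, gastrointestinal, endocrine and pulmonary categories but no hepatic rate. The rate also covers Grade 3 and 4 events, not a laboratory band. No count can be derived.

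The conclusion rests on the Grade 2 ranges in Section 7.4.1.1 for the start of Grade 3, and on the assumption that 8 x ULN lies within Grade 3.

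**What to change.** Reconcile Section 7.4.1, Section 8.1.1.1 with its footnote, Section 8.1.1.2 and Section 8.1.3 so that one liver discontinuation rule is stated for each drug. The text should say:

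- whether the footnote overrides Section 7.4.1;
- whether the footnote covers bilirubin, given where its asterisk sits;
- how the footnote interacts with the ipilimumab limits in Section 8.1.1.2.

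Sections 7.4.1 and 8.1.3 should then point to that rule instead of restating it with different force. Section 8.1.3 also refers to Appendix 7 for liver conditions. In this version that appendix is the country-specific amendment and the management algorithms are in Appendix 8, so the reference can be corrected at the same time.

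Which rule and which thresholds apply is for the sponsor's safety physicians to decide; this review takes no view. The cost is a text amendment and a letter to sites, with no new assessments or data.
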